2.3.1.2 STUDY PARTICIPATION

2.3.1.2.1 Returning Results

All medically relevant results, which might impact the future diagnosis or treatment of the participant will be provided to the participant and the site PI. With the exception of results from amyloid PET, it is the general policy of this study not to reveal research results to participants; however, if information is obtained that the site PI (or medically qualified designee) determines to be medically relevant, such information may be shared. For example, results from cognitive testing may be shared as part of a dementia diagnosis. Similarly, MRI scan findings of clinical significance, as determined by either the central read or local read, may be shared with the participant. Additionally, the site PI may also return clinical labs from the clinical visit.

In general, genetic and biomarker (including blood and CSF) samples are for research purposes only, not diagnostic, and will not be revealed to clinic staff or the participant. An exception will be allowed if the participant wishes to enroll in a treatment trial or requires the genetic or blood/CSF information to receive treatment.

The Neuropathology Core, described in section 9.1.1, will provide a neuropathology report to the site PI to return to families of those who register for brain donation and wish to review these findings.

Returning Amyloid Status:

Participants will be given the option of learning the results from their amyloid PET imaging. If a participant so chooses, those results will be disclosed as described in relevant study manual. Participants who receive a positive or elevated result may believe that the person is going to develop Alzheimer's disease dementia, which, in turn, could cause psychological distress and an experience of stigma. In contrast, participants who received a negative result may experience a mistaken belief that they will never develop AD, or they may develop concern born of the uncertainty that they have some but not enough amyloid.

2.3.1.2.2 Genetic

NIH policy requires that de-identified genomic data is uploaded to a secure government sponsored health research database for broad sharing with approved investigators. This information will be de-identified and will not contain any traditional identifiers. There is a slight risk that there could be a breach in the security of this database system resulting in the unauthorized access to de-identified information. Safeguards at the government health database are in place to minimize this risk.

Another possible risk from participation in this study involves a loss of privacy as a result of providing genetic material (nucleic acids) for research. Although genetic information is unique to each individual it is also shared with their children, parents, brothers, sisters, other blood relatives and other members of their ethnic group. Methods to allow someone to link the genetic or medical information back to the study participant could be developed in the future but authorized users agree to not to attempt to identify any study participants.

2.3.1.2.3 Loss of Privacy

In this study, a great deal of information about participant health status will be collected. Study staff personnel will collect personal protected health information such as name, date of birth, address, phone number, and emails. Each study staff will maintain the personal protected health information in a secure and locked location. All participants will be assigned a PTID and all data collected under this protocol will be associated with that PTID. The data, associated with the PTID, will be shared widely, but it will not be possible to identify an individual participant from the data. However, there is a very unlikely possibility of a security failure, in which case the protected health information will be no longer protected. This is an extremely unlikely, but possible, occurrence and is a risk of this study (and almost all other medical research studies).

To protect participant privacy from facial imaging identification, MRI and PET scans will undergo defacing prior to public release. Individuals could request access to non-defaced images but would need to justify the specific need and may need to sign a stronger data privacy agreement.

Participants will be asked to share personal protected health information such as name, date of birth, address, phone number, and email address. Participants will be assigned a study identification code for the data collected in the remote digital and blood cohorts. The collected data will be maintained on ADNI Admin Core secure servers. Additionally, audio recordings of participants' voices will be collected for analysis of cognitive digital biomarkers using the Novoic Ltd. Testing Platform, and audio files will be stored on secure, HIPAA compliant servers.

All deidentified data will be shared through the ADNI LONI website, with the exception of audio files which will not be available for download, but anonymized transcripts will be available. In order to obtain ADNI data, investigators must sign a "Data Use Agreement" which prohibits any attempts to identify the study participants. The agreement also prohibits any subsequent transfer of ADNI data.

Speech recordings, transcripts, and other measures extracted from the speech recordings and transcripts will be stored in secure databases and shared with other, carefully selected parties, including Novoic Ltd. These can be used for research and to develop better measures of brain health, including training machine learning algorithms. Sharing of speech recordings will be subject to a separate data use agreement to better safeguard participant privacy.

2.3.1.2.4 GUIDs

ADNI4 will be incorporating Global Unique Identifiers (GUIDs) for all ADNI participants. Each GUID unambiguously identifies a research study participant across different research studies without exposing protected health information (PHI). When investigators pool data together from multiple studies, GUIDs provide the means to detect participants who participate in more than one study.

ADNI sites will download a GUID generator to convert participant PHI (e.g., birth name, birth date, place of birth) into irreversible hash codes. These hash codes will be sent to the GUID authority operated by NIA, which will assign GUIDs and store them along with ADNI participant information in the clinical database. Sites will use the currently adopted GUID generator, known as the NINDS Centralized GUID solution, developed by The National Institute of Neurological Disorders & Stroke (NINDS), in conjunction with the National Institute of Aging (NIA), and the Parkinson's Disease Biomarkers Program (PDBP) using the Biomedical Research Informatics Computer System (BRICS) platform.

3 OBJECTIVES AND ENDPOINTS

ADNI4 will continue to discover, optimize, standardize, and validate clinical trial measures and biomarkers used in AD research. ADNI4 will address low rates of engagement and inclusion of underrepresented populations (URPs) in AD clinical cohorts. The ADNI4 in-clinic cohort will include up to 750 new participants as well as up to 750 rollover participants from ADNI3.

Aim 1: Validation of biomarker measures

Validate biomarker measures obtained at baseline and longitudinally by correlating results with "gold standard" clinical measurements and pathology.

Aim 2: Inform clinical trial design

Determine the optimum outcome measures with attention to cognitive decline and tau/amyloid PET, predictors of cognitive decline, and inclusion/exclusion criteria for clinical trials of cognitively normal participants (for secondary preclinical AD trials), MCI patients (for prodromal AD trials) and participants with early dementia due to AD.

Aim 3: Increased inclusion of underrepresented populations (URPs) to improve generalizability of results, and advance our understanding of health disparities across URPs.

ADNI4 will recruit 50-60% URPs using community-engaged research strategies with culturally tailored outreach, including digital marketing. This will produce more generalizable data concerning the relationships of biomarkers and pathology to cognitive decline and dementia across ethnocultural groups.

Aim 4: Utilize blood-based biomarkers to remotely identify and monitor those with AD biomarker pathology

Recent developments in plasma biomarkers for the AD pathophysiologic cascade have the potential to lower the cost of AD research, improve the feasibility of clinical trials, and vastly expand access to previously excluded groups. However, many of these novel analyses require further validation, and ADNI4 will contribute to this research by collecting blood samples from participants using local phlebotomy service centers. Blood will be analyzed for multiple AD biomarkers (amyloid, tau, APOE) and resulting data

will be compared with other biomarker data (clinical/cognitive, MRI, PET, etc.) to help validate the utility of these biomarkers for future trials.

Aim 5: Longitudinal changes in cognition and associated biomarkers

Determine and define those measures of cognition and function, including composite measures, and biomarker measures, which capture longitudinal change with the highest statistical power to detect treatment effects in clinical trials. Longitudinal change of cerebral amyloid and tau measured with FBP, FBB, NAV4694, and FTP, MK6240, and PI2620, respectively, will be correlated/compared with other measures including use of novel plasma biomarkers.

Aim 6: Prediction of cognitive decline

Determine which clinical, cognitive, and biomarker measures best predict cognitive decline in CN, MCI, and DEM participants. In addition, determine which biomarker changes correlate with cognitive decline, with a focus on plasma biomarkers, as well as amyloid and tau PET.

Aim 7: Discovery of novel risk and protective genes and pathways, and other known disease proteins found in AD brains.

To determine the effects of other known disease proteins found in AD brains and genes, as well as newly discovered genes, proteins, and analytes that provide useful information concerning the pathogenesis/diagnosis of AD.

4 STUDY DESIGN

4.1 OVERALL DESIGN

This is a non-randomized, natural history, non-treatment study. Clinical and cognitive testing, imaging, biomarkers and genetics will be assessed across 3 diagnostic groups: CN, MCI, and DEM.

For in-clinic assessments, MCI and DEM will be seen annually, CN participants every other year. Remote assessments (per SoE) will be conducted 2x/year for CN and MCI; remote assessments will not be conducted for DEM participants.

Visit frequency and assessments are outlined in more detail in Description of Study Visits and SoE.

4.1.1 SAMPLE SIZE

Up to 1,500 participants will be enrolled to the in-clinic cohort of ADNI4 at approximately 65 sites in the United States and Canada. Up to 750 will be rollover participants from ADNI3, and up to 750 will be newly enrolled. Clinical/cognitive, imaging, biomarker, and genetic characteristics will be assessed across the three cohorts: CN, MCI, and DEM.

4.1.1.1 ROLLOVER IN-CLINIC PARTICIPANTS

ADNI4 is targeting to retain at least 75% of the ADNI3 Cognitively Normal (CN) cohort, 50% of the symptomatic Mild Cognitive Impairment (MCI) cohort, and 15% of those with dementia (DEM).

4.1.1.2 NEW IN-CLINIC PARTICIPANTS

ADNI4 is aiming to include up to 750 new participants for the in-clinic cohort with at least 50-60% URPs, and target diagnostic categories of at least 40% CN, 40% MCI, 20% DEM, and overall, an 80% amyloid positive rate.

4.2 END OF STUDY DEFINITION

18

A participant in the in-clinic cohort is considered to have completed the ADNI4 study if they have completed all phases of the study including the last visit or the last scheduled procedure shown in the SoE, Section 1.3.

The end of the study is defined as completion of the last visit or procedure shown in the SoE in the study globally.

5 STUDY POPULATION

The study will enroll people aged 55-90 years across the remote digital cohort, remote blood cohort and the in-clinic cohort, as specified in the entry criteria below. Exceptions to these guidelines may be considered on a case-by-case basis at the discretion of the project director and ADNI-Clinical Core.

Inclusion/Exclusion criteria for the in-clinic cohort are detailed in the tables below. The criteria aims to increase generalizability of ADNI findings by increasing flexibility (e.g., around study partner requirements and need to complete lumbar punctures and all imaging procedures), relaxing some medical restrictions (particularly around vascular comorbidity) and allowing newly FDA approved and clinically available disease-modifying treatments.

5.1 INCLUSION CRITERIA

5.1.1 INCLUSION CRITERIA FOR THE IN-CLINIC COHORT

5.1.1.1 NEWLY ENROLLED PARTICIPANTS

	CN	MCI	DEM
1.	Participant may or may not have a significant subjective memory concern as reported by participant, study partner, or clinician.	Participant must have a subjective memory concern as reported by participant, study partner, or clinician.	Same as MCI
2.	Normal memory function documented by scoring above demographically-adjusted cutoffs on the Logical Memory II subscale (Delayed Paragraph Recall, Paragraph A only) from the Wechsler Memory Scale − Revised (the maximum score is 25): a. ≥9 for 16 or more years of education b. ≥ 5 for 8-15 years of education c. ≥ 3 for 0-7 years of education d. Note: cut-offs may be modified over time as the field evolves in this area	Abnormal memory function documented by scoring within the demographically-adjusted ranges on the Logical Memory II subscale (Delayed Paragraph Recall, Paragraph A only) from the Wechsler Memory Scale − Revised (the maximum score is 25): a. ≤11 for 16 or more years of education b. ≤9 for 8-15 years of education c. ≤6 for 0-7 years of education. d. Note: cut-offs may be modified over time as the field evolves in this area.	Same as MCI
3.	Mini-Mental State Exam score between 24 and 30 (inclusive) (Exceptions may be made for participants with less than 8 years of education at the discretion of the Project Director and/or Clinical Core)	Same as CN	Mini-Mental State Exam score between 20 and 28 (inclusive) (Exceptions may be made for participants with less than 8 years of education at the discretion of the Project Director and/or Clinical Core)

v1.0

4.	Clinical Dementia Rating = 0. Memory Box score must be 0.	Clinical Dementia Rating = 0.5. Memory Box score must be at least 0.5	Clinical Dementia Rating = 0.5 or 1.0.
5.	Cognitively normal, based on an absence of significant impairment in cognitive functions or activities of daily living.	General cognition and functional performance sufficiently preserved such that a diagnosis of dementia cannot be made by the site physician at the time of the screening visit.	Meets the National Institute on Aging/Alzheimer's Association Diagnostic Guidelines for Dementia (2011)
6.	Stability of Permitted Medications for 4 weeks. In particular, participants may: a. Take stable doses of antidepressants lacking significant anticholinergic side effects (if they are not currently depressed and do not have a history of major depression within the past 1 years) b. Estrogen replacement therapy is permissible c. Gingko biloba is permissible, but discouraged d. Washout from psychoactive medication (e.g., excluded antidepressants, neuroleptics, chronic anxiolytics or sedative hypnotics, etc.) for at least 4 weeks prior to screening.	Stability of Permitted Medications for 4 weeks. In particular, participants may: a. Take stable doses of antidepressants lacking significant anticholinergic side effects (if they are not currently depressed and do not have a history of major depression within the past 1 year) b. Estrogen replacement therapy is permissible c. Gingko biloba is permissible c. Gingko biloba is permissible, but discouraged d. Washout from psychoactive medication (e.g., excluded antidepressants, neuroleptics, chronic anxiolytics or sedative hypnotics, etc.) for at least 4 weeks prior to screening e. Cholinesterase inhibitors and memantine are allowable if stable for 12 weeks prior to screen f. Aducanumab and any other approved treatments for the neurobiology of AD if stable for 24 weeks prior to screen	Same as MCI

Additional inclusion criteria that apply to all diagnostic categories for newly enrolled participants:

- 1. Geriatric Depression Scale score less than 10.
- 2. Age between 55-90 years (inclusive).
- 3. Study partner who has frequent contact with the participant (i.e., minimum average of 2 hours per week) and may be able to accompany the participant to clinic visits or provide information remotely

(e.g. over the phone).

- 4. Visual and auditory acuity adequate for neuropsychological testing.
- 5. Good general health with no diseases expected to interfere with the study.
- 6. Participant is not pregnant, lactating, or of childbearing potential (i.e., women must be two years post-menopausal or surgically sterile).
- 7. Willing and able to participate in a longitudinal imaging study.
- 8. Must be literate and speak English or Spanish fluently.
- 9. Agrees to collection of blood for GWAS, APOE testing, DNA and RNA testing
- 10. Agrees to collection of blood for biomarker testing.
- 11. The Administrative Core, described in section 9.1.1, will collaborate with leadership from all Cores to review the blood biomarker data from the remote blood cohort and select participants to join the in-clinic cohort. See ADNI4: Remote protocol.
- 12. Agrees to participate in the ADNI study which includes cognitive evaluation, MRI and PET scans.
- 13. Flexibility can be made to all criteria for those with at least 8 years in a low socio-economic status (SES) neighborhood.

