1.3 SCHEDULE OF EVENTS (SOE)

1.3.1 NEWLY ENROLLED PARTICIPANTS (CN, MCI, DEM)

CN participants receive a phone check at Month 12 and Month 36. CN participants are seen in the clinic at Screening/Baseline and then biennially (every other year) at Month 24 and Month 48. Refer to the relevant study manual for a description of assessments conducted at phone checks.

MCI and Converter participants are seen in the clinic annually.

DEM participants are seen in-clinic for 24 months from Baseline (total of 3 in-clinic visits at Baseline, Month 12, and Month 24) and then ongoing phone follow-up.

ADNI4 Visit Activity	Screening	Baseline	12 Mon	24 Mon	36 Mon	48 Mon
Obtain consent	Х					
Phone Check			X ¹		X ^{1,2}	X ²
GUID Creation	Х					
Neuropath discussion/Provisional Registration ³	X	Х	Х	X	X	Х
Demographics, Family History, Medical History	X					
Inclusion and Exclusion Criteria	Х					
Physical Exam, Neurological Exam	Х		Χ	X	Х	X

Vital Signs	Х	Х	Х	X	Х	X
Height	Х					
Initial Labs (hematology, Chemistry panel, urinalysis, B12, TSH, HgbA1c, high sensitivity CRP)	X					
Hollingshead Index Score	Х					
Area Deprivation Index (ADI)		Х				
Abbreviated Multidimensional Acculturation Scale (AMAS) ⁴		X				
American National Adult Reading Test (AMNART)		Х				
Mini Mental State Examination (MMSE)	Х		X	Х	X	X
Logical Memory I and II	X		X	X	X	X
Montreal Cognitive Assessment (MoCA)		X	X	Х	Х	X
Category Fluency Test (CFT)		Х	Х	X	X	X
Trails A & B		X	X	Х	X	X
Multi-Lingual Naming Test (MINT)		Х	X	X	X	X
Auditory Verbal Learning Test		X	X	Х	X	X
Geriatric Depression Scale (GDS)	X		X	X	X	X
Clock Drawing Test		X	X	Х	X	X
Neuropsychiatric Inventory (NPI) / (NPI- Q for Phone Check)		Х	X	X	X	Х
ADAS-Cog 13 (w/Delayed Recall and Number Cancellation)		Х	X	X	X	X
Clinical Dementia Rating (CDR)	X		X	X	X	X
Perceived Stress		X	X	X	X	X
Perceived Discrimination		X	Х	X	X	X
Functional Assessment Questionnaire (FAQ)		X	X	X	X	X
12-Item ECog (in-clinic) ⁵		X	X	X	X	X
Plasma and Serum Biomarker Sample Collection ⁶		X	X	Х	X	Х
PMBC Sample Collection ⁶		Х				
Lipid Panel ⁶		X				
DNA Sample Collection ⁶		Х				
Ongoing Labs (HgbA1c, Cystatin C, Creatinine, BUN)		Х	X	X	X	X
RNA and Buffy Coat Sample Collection ⁶		X	X	X	X	X
Concomitant Medications	X	X	X	X	X	X
Adverse Events	X	Х	X	X	X	X
Diagnostic Summary	X	X	X	X	X	X
Remote Assessments (Novoic Storyteller & 12-Item ECog) ⁷		X	Х	Х	X	X
Pregnancy Test ⁸		X		X		X
3T MRI Imaging ⁹	Х		X	X	X	X
Tau PET Imaging		X		X		X ²
Amyloid PET Imaging		Х		X		X ²

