8.2 STATISTICAL ANALYSIS GOALS

Goal 1: To support the design of the ADNI4 cohorts, particularly the remote blood and in-clinic cohorts. Participant referrals will be informed by results from the remote digital cohort components (questionnaire, cognitive testing) and the plasma-based AD biomarkers to ensure sample diversity for those selected for in-clinic participation, to allow testing of hypotheses and to increase generalizability to a larger population.

Goal 2: Characterize baseline distribution of biomarkers and associations. Baseline characteristics will be summarized graphically and numerically, separately for baseline diagnostic categories (CN, MCI, DEM). Associations among biomarkers and with cognitive, clinical, and functional levels at baseline will be summarized numerically and graphically. Performance of baseline biomarkers as predictors of cognitive and functional change, disease progression, and post-mortem findings will be assessed by regression models (linear, logistic, survival, etc.).

Goal 3: Assess the potential of biomarkers for use in screening, inclusion/exclusion, stratification, and covariate adjustment for clinical trials. We will report and compare predictive abilities and impact on sample size, power, and duration of study in hypothetical clinical trials. To assess the explanatory power of a candidate biomarker, we will build models incorporating additional variables (demographics, genotype, baseline clinical or cognitive status, additional biomarkers). Sex as a biological variable will be considered both as a predictor and a potential effect modifier.

Goal 4: Characterize longitudinal trajectories of biomarkers and their associations. Longitudinal change in biomarkers will be characterized using linear mixed models for continuous measures, possibly transformed to deal with floor or ceiling effects, nonlinearity, practice effects, nonnormality, or heteroscedasticity. Extensions of these models allow for the simultaneous modeling of change in multiple outcomes for estimating correlation between change in multiple biomarkers or change in a biomarker with cognitive and functional change.

Goal 5: Assess the potential associations of comorbidities and sociocultural factors with biomarker, cognitive, and functional levels and longitudinal change. We hypothesize that ethnocultural differences will be associated with differences in baseline levels and

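### In new participants the Logical Memory II score that admits them is also their only scheduled time-zero value, so regression to the mean can distort Aim 5's comparison of cognitive measures

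*Protocol*

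**What the plan says.** **Entry (section 5.1.1.1, criteria 2 to 4).** New MCI participants must show "Abnormal memory function documented by scoring within the demographically-adjusted ranges on the Logical Memory II subscale"; the DEM column refers to the same rule. The limit at the highest education level is "≤11 for 16 or more years of education", with 9 and 6 at the two lower levels. For CN it is "≥9 for 16 or more years of education", with 5 and 3 below that. MMSE must lie in 24–30 for CN and MCI and in 20–28 for DEM. CDR is restricted by group.

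**Schedule (section 1.3.1).** The row "Logical Memory I and II" is marked at Screening, blank at Baseline, and marked again from Month 12. MMSE and CDR follow the same pattern. CN participants have phone checks at Months 12 and 36, so their next clinic scores come at Months 24 and 48. DEM participants have clinic visits up to Month 24. ADAS-Cog 13, MoCA and AVLT are first given at Baseline and are not entry criteria. Section 7.1.4 leaves the Baseline list to the schedule, and section 7.1.3 allows repeat screening tests only by exception.

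**Use.** Aim 5 (section 3) seeks the cognitive, functional and biomarker measures "which capture longitudinal change with the highest statistical power to detect treatment effects in clinical trials". Goal 4 (section 8.2) describes change "using linear mixed models for continuous measures" and mentions floor, ceiling and practice effects, but not selection on the first score.

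**Rollovers.** They have no Screening visit, and section 5.1.1.2 sets them no score cut-off.

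**The concern.** A score that must fall on one side of a limit carries, on average, a measurement error in that direction. At the next visit the error is fresh, and the group mean moves back with no true change. For Logical Memory this is a rise in MCI (upper limit) and a fall in CN (lower limit).

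Because the admitting score is also the first point of the slope, the artefact enters estimated decline directly. A measure first taken at Baseline, such as AVLT, does not carry its own selection error. A comparison of Logical Memory with AVLT would then partly reflect which test was used for screening. The CN–MCI difference in Logical Memory slope would be affected from both sides.

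The mixed model does not remove this by itself. A likelihood analysis could do so if everyone screened contributed a score, but section 5.3 requires only minimal data on screen failures and does not list test scores among them.

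**Working it through.** The protocol states no SD, reliability, slope or power, so there is no figure of its own to reproduce. The entry limits and visit times below are the protocol's; all other inputs are assumptions.

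**1. Shift from Screening to a retest with no true change.** Let ρ be test–retest reliability, and let φ and Φ be the standard normal density and distribution function. With a half-point continuity correction:

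- Upper limit c: shift = +(1−ρ)·SD·φ(a)/Φ(a), where a = (c + 0.5 − mean)/SD.
- Lower limit c: shift = −(1−ρ)·SD·φ(a)/(1−Φ(a)), where a = (c − 0.5 − mean)/SD.
- Both limits: shift = −(1−ρ)·SD·(φ(a) − φ(b))/(Φ(b) − Φ(a)), with a at the lower limit and b at the upper.

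Taking ρ from 0.6 to 0.8:

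| Test and group | Limit | Assumed pool mean; SD | Shift (points) |
|---|---|---|---|
| Logical Memory II, MCI | ≤11 | 8–10; 4.5 | +0.34 to +1.08 |
| Logical Memory II, MCI | ≤9 | 8–10; 4.5 | +0.54 to +1.57 |
| Logical Memory II, CN | ≥9 | 10–12; 4–4.5 | −0.27 to −1.08 |
| Logical Memory II, CN | ≥9 | 12–14; 4 | −0.14 to −0.54 |
| Logical Memory II, CN | ≥5 | 10–12; 4–4.5 | −0.06 to −0.38 |
| Logical Memory II, DEM | ≤11 | 3–5; 3.5 | +0.01 to +0.10 |
| MMSE, MCI | ≥24 (30 is the scale maximum) | 26.5–27.5; 2.2 | −0.04 to −0.15 |
| MMSE, DEM | 20–28 | 22–23.5; 3 | −0.05 to −0.37 |

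**2. Weight of time zero in a least-squares slope.** The weight is (t₀ − t̄)/Σ(t − t̄)²:

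- MCI, years 0, 1, 2, 3, 4: −2/10 = −0.20.
- CN, years 0, 2, 4: −2/8 = −0.25.
- DEM, years 0, 1, 2: −1/2 = −0.50.

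The slope bias is the shift times the absolute weight. For MCI at ≤11 with mean 10 and ρ = 0.7, the shift is +0.81 and the bias is 0.81 × 0.20 = +0.16 per year. A true slope of −0.60 is then estimated as −0.44.

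**3. Simulated slopes and implied trial size.** The simulation used the admitting score as time zero, then an independent remeasurement. Trial size is per arm for 25% slowing, two-sided alpha 0.05 and power 0.80. Assumed SDs of the true slope were 0.8 (Logical Memory in MCI and DEM, MMSE in MCI), 0.4 (Logical Memory in CN) and 1.5 (MMSE in DEM).

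| Case | True slope per year | Estimated slope | n per arm, ratio to remeasured |
|---|---|---|---|
| Logical Memory, MCI ≤11 (mean 8–10) | −0.60 | −0.38 to −0.53 | 1.25 to 2.33 |
| Logical Memory, CN ≥9 (mean 12–14) | −0.10 | −0.13 to −0.24 | 0.17 to 0.56 |
| Logical Memory, DEM ≤11 | −0.80 | −0.75 to −0.79 | 1.01 to 1.12 |
| MMSE, MCI | −0.70 | −0.71 to −0.73 | 0.91 to 0.98 |
| MMSE, DEM | −2.0 | −2.02 to −2.19 | 0.80 to 0.96 |

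For MCI with mean 10 and ρ = 0.7, n per arm is 1,597 instead of 867. CDR was not simulated.

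**4. Price of leaving out time zero.** The residual-error part of slope variance is proportional to 1/Σ(t − t̄)². That sum falls from 8 to 2 in CN (Months 24 and 48 remain), from 2 to 0.5 in DEM (Months 12 and 24 remain) and from 10 to 5 in MCI. This part of the variance therefore grows 4-fold, 4-fold and 2-fold.

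**The case against.** **This belongs in an analysis plan.** Section 8.1 says it only summarizes strategies and promises secondary analyses of sensitivity and robustness; a plan not shown could deal with the first score. That is fair for modelling detail. But the single administration is fixed in this protocol, and Goal 4 already names the nuisance effects it expects without this one. An all-visit model that follows the text would carry the bias.

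**The size is assumed.** This stands. For CN at the ≥9 limit, moving the assumed pool mean from 10–12 to 12–14 roughly halves the shift. New participants may also come through remote selection that includes a story-recall test (section 7.2.1), which the calculation does not model. The exceptions allowed in sections 5 and 5.1.1.1 soften the limits without removing them.

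**Stronger readings do not hold.** A reader might infer that all three entry tests are distorted alike, with scores rising in MCI and DEM. The MMSE limits say otherwise: MCI is bounded from below, and DEM mainly so under the assumed means, so MMSE regresses downwards. A reader might also infer that Goals 3 and 6 are undermined throughout. As worded, those goals concern biomarkers; it is Aim 5 that expressly lists measures of cognition. Nor does the point require replacing the main analysis, because dropping time zero costs much precision.

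**Rollovers are not a clean control.** Section 5.1.1.2 requires at least a year in an earlier ADNI study, and the retention targets in section 4.1.1.1 are 75% of CN, 50% of MCI and 15% of DEM. Prior test exposure and selective retention would confound a repeat in that group.

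**Conclusion.** The concern holds for Logical Memory in newly enrolled MCI and CN participants. On the assumed inputs, Logical Memory decline is understated by about 12–37% in MCI and overstated by about 30–140% of a small assumed slope in CN. Opposite errors of this size could change where Logical Memory ranks against AVLT, ADAS-Cog 13 or MoCA.

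Elsewhere the effect is lesser: MMSE decline is overstated by about 1–4% in MCI and 1–10% in DEM, and Logical Memory in DEM is understated by about 1–6%. Nothing is claimed about the size for CDR. Pooling with up to 750 rollovers dilutes the effect. The directions for Logical Memory follow from the entry limits and the schedule; every size depends on the assumed pool means, SDs, reliability and slopes. The protocol contains no false statement here. This is a foreseeable bias with a cheap check.

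**What to change.** Keep the all-visit mixed model as the main analysis. Add to section 8.2 a pre-stated sensitivity analysis, in newly enrolled participants, that repeats the ranking of cognitive outcome measures in one of two ways:

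- exclude the time-zero value for every measure, Screening and Baseline scores alike, so that all measures use the same clinic visits from Month 12 on; or
- keep all visits and include a time-zero indicator by diagnostic group.

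Report whether the ranking changes. Removing only the Screening scores would not do: the tests first given at Baseline would keep one more time point than the entry tests. A repeat in rollovers can be shown as supportive only.

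The cost is analysis wording and some programming, with no new visits or tests. The downside is less precise sensitivity slopes, most of all in CN and DEM, where two clinic visits remain. A changed ranking there should be read alongside its interval estimates.
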